6.2. Laboratory Assessments

All laboratory assessments will be performed locally. The laboratory must provide normal reference ranges for hematology, chemistry, and coagulation tests. If justified (eg, deterioration of the patient's health conditions and/or distance from the clinical site) and allowed by the country and institution, laboratory tests performed by external laboratories may be used for the study. However, laboratory reference ranges and accreditation are required. All laboratory test results (internal or external) must be reviewed for clinical significance by the Investigator.

Any clinically significant events must be followed and reported as required by the protocol (please see [Section 9.3.1](#)).

7.

CCI

CCI

Table 10: CCI

Day of Study (Time Window)	Collection Time Point (hours) in Relation to Futibatinib Administration (Time Window)
CCI	

8. EFFICACY EVALUATIONS

Efficacy parameters will be assessed based on on-site tumor assessments (including computed tomography [CT] or magnetic resonance imaging [MRI] if CT scan is not feasible) performed by the Investigator/local radiologist according to RECIST 1.1 guidelines [Eisenhauer et al. 2009]).

In addition to RECIST 1.1, iRECIST will be used. iRECIST is based on RECIST 1.1, but adapted to account for the unique tumor response seen with immunotherapeutic drugs. iRECIST will be used by the Investigator to assess tumor response and progression, and make decisions regarding the continuation of study treatment.

If the Investigator determines that a patient has developed clinical disease progression manifested by symptomatic deterioration but not supported by radiologic evidence of progression, the patient may stop treatment. Symptoms of clinical disease progression must be documented in the patient's source documents and must be reported as AEs.

Patients who discontinue without documented PD per RECIST 1.1 should continue to undergo tumor assessments/scans according to the study schedule until PD is documented per RECIST 1.1, new anticancer therapy is initiated, the study is terminated, or consent is withdrawn.

8.1. Evaluation of Efficacy per RECIST 1.1

8.1.1. Method of Imaging

The same method of assessment and same technique should be used to characterize each identified and reported lesion at each assessment timepoint. Imaging-based evaluation is preferred to evaluation by clinical examination when both methods have been used to assess the antitumor effect of treatment. All measurements should be recorded in metric notation using a ruler or calipers.

Contrast-enhanced CT scans or MRIs are the preferred methods for tumor assessments. If a contrast agent is contraindicated in a patient, obtain a non-contrast chest CT and enhanced MRI of the abdomen (and pelvis if clinically indicated). A spiral CT should be performed using a ≤ 5 mm contiguous reconstruction algorithm. Images must be acquired of the chest and abdomen (and pelvis if clinically indicated or obtained at Baseline) at each time point. Only CT scans and MRI may be used for tumor measurement.

Clinical lesions will only be considered measurable when they are superficial (eg, skin nodules, palpable lymph nodes). In the case of skin lesions, documentation by color photography, including a ruler to estimate the size of the lesion, is recommended.

Ultrasound should not be used to measure tumor lesions that are clinically not easily accessible for overall response evaluation (for example, visceral lesions). Ultrasound is a possible alternative to clinical measurements of superficial palpable nodes, subcutaneous lesions, and thyroid nodules. Ultrasound might also be useful to confirm the complete disappearance of superficial lesions usually assessed by clinical examination. For additional guidance, refer to RECIST 1.1 specifications for standard anatomical radiological imaging.

8.1.2. Tumor Definitions

Measurable Lesions: Only measurable lesions can be selected as target lesions.

- Measurable visceral lesions: Lesions that can be accurately measured in at least 1 dimension with the longest diameter (to be recorded) ≥ 10 mm by CT scan if using slice thickness of ≤ 5 mm, or at least double the slice thickness of the CT or MRI scan if the slice thickness is > 5 mm.
- Measurable pathological lymph nodes: A malignant lymph node must be considered pathologically enlarged with high suspicion of metastasis and measure ≥ 15 mm in the short axis when assessed by CT scan. The short axis is defined as the longest linear dimension perpendicular to the node's longest diameter as assessed within the same plane that the scan was acquired.

Non-measurable Lesions: All non-measurable lesions can only be selected as non-target lesions.

- Small visceral metastatic lesions that have a longest dimension < 10 mm, or if slice thickness is > 5 mm, less than twice the slice thickness
- Abnormal and suspected metastatic lymph nodes that are ≥ 10 mm to < 15 mm in the short axis
- Truly non-measurable lesions (eg, ascites and peritoneal carcinomatosis)

Target Lesions:

- All measurable lesions up to a maximum of 2 lesions/organ and 5 lesions in total, representative of all involved organs/tissues should be identified as target lesions
- Target lesions should be selected on the basis of their size (visceral lesion with the longest diameter and lymph node with the measurement of short axis), be representative of all involved organs/tissues, but in addition should be those that lend themselves to reproducible repeated measurements
- When recording tumor measurements, the longest diameter will be measured for each non-nodal target lesion. For measurable pathological lymph nodes that may be identified as target lesions, the short axis measurement will be combined with the measurements of non-nodal (ie, visceral lesion) target lesions. Therefore, in cases of CR when abnormal nodes have been used as target lesions, the sum of diameters will not reduce to a null value.
- Target lesions will be followed up and measured at each subsequent timepoint.
- The sum of the diameters for all target lesions will be calculated and recorded. The baseline sum will be used as a reference to further characterize any objective tumor assessment in the measurable dimension of the disease.
- Assign a measurement to all target lesions regardless of size. An option of “too small to measure” will be provided if a measurement cannot be assigned. A value of zero should only be assigned in the case of a CR.
- An option of “not assessable” for a lesion will only apply to lesions that cannot be read due to technical reasons including:

- CT artifact
- Patient positioning where the lesions are obstructed or cannot be seen
- Lesions that may not be seen in their entirety due to CT slice thickness
- In cases where a lesion divides into 2 lesions, the longest diameters of the fragmented portions should be added together to calculate the target lesion sum.
- In cases where 2 lesions coalesce, a plane between them may be maintained that would aid in obtaining maximal diameter measurements of each individual lesion. If the lesions have truly coalesced such that they are no longer separable, the vector of the longest diameter in this instance should be the maximal longest diameter for the “coalesced lesion.”

Non-target Lesions:

- Non-target lesions include all non-measurable lesions and measurable lesions that have not been selected as target lesions.
- The primary lesion should always be classified as a non-target lesion irrespective of its size and whether or not it can be accurately measured.
- Lymph nodes that have a short axis <1 mm are considered non-pathological and should not be recorded.
- Any equivocal lesion without clear diagnosis (eg, uncharacteristic solitary lung nodule without biopsy, uncharacteristic thyroid mass lesion without fine needle aspiration) may be considered a non-target lesion if it cannot be differentiated from a benign lesion.
- All other lesions (or sites of disease), including pathological lymph nodes, should be identified as non-target lesions and should also be recorded at Baseline. Measurements are not required, but their presence, absence, or unequivocal progression should be followed throughout the study.
- It is possible to record multiple non-target lesions involving the same organ as a single item on the electronic case report form (eCRF) (eg, multiple enlarged pelvic lymph nodes or multiple liver metastases).

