4. SELECTION AND WITHDRAWAL OF PATIENTS

4.1. Inclusion Criteria

A patient must meet all of the following criteria to be eligible for participation in this study; waivers will not be granted for any of the eligibility criteria.

1. Histologically confirmed advanced or metastatic UC in patients who have not received systemic treatment for advanced metastatic disease. For patients who received prior adjuvant/neoadjuvant chemotherapy or chemo-radiation for urothelial carcinoma, a treatment-free interval >12 months between the last treatment administration and the date of recurrence is required in order to be considered treatment-naïve in the metastatic setting.
 - a. In safety lead-in: enrollment regardless of FGFR status
 - b. Cohort A: must have an *FGFR3* mutation or *FGFR1-4* fusion/rearrangement
 - c. Cohort B: all other patients with UC (including patients with other FGFR or non-*FGFR* genetic aberrations and patients with WT [nonmutated] tumors)
2. Unfit for or intolerant to standard platinum-based chemotherapy as defined by any one of the following criteria:
 - a. Chronic kidney disease characterized by the estimated creatinine clearance rate (eCCr) per Cockcroft-Gault formula of <60 mL/min or estimated glomerular filtration rate (eGFR) of <60 mL/min/1.73 m², corresponding to NCI-CTCAE v.5.0 Grade ≥ 2
 - b. Impaired hearing (measured by audiology) of >25 dB at two contiguous test frequencies in at least one ear, corresponding to NCI-CTCAE v.5.0 Grade ≥ 2
 - c. Peripheral sensory neuropathy Grade ≥ 2 by NCI-CTCAE v.5.0
 - d. Patient refusal
 - e. In the opinion of the Investigator, the patient is considered ineligible to receive any platinum-based chemotherapy
3. Be willing and able to provide written informed consent for the trial.
4. Be ≥ 18 years of age.
5. Have an Eastern Cooperative Oncology Group (ECOG) performance status (PS) of 0 to 1.
6. Adequate organ function as defined by the following criteria:
 - a. Absolute neutrophil count (ANC) $\geq 1.5 \times 10^9/L$
 - b. Platelet count $\geq 100,000/mm^3$
 - c. Hemoglobin $\geq 9.0 \text{ g/dL}$
 - d. Alanine aminotransferase (ALT) and aspartate aminotransferase (AST) $\leq 2.5 \times$ upper limit of normal (ULN); if liver function abnormalities are due to underlying liver metastasis, AST and ALT $\leq 5.0 \times$ ULN.

- e. Total bilirubin $\leq 1.5 \times$ ULN, or $\leq 3.0 \times$ ULN for patients with Gilbert's syndrome.

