- f. Creatinine clearance (Ccr) (calculated or measured value): ≥ 30 mL/min. For calculated Ccr, use the Cockcroft-Gault formula.
- g. International normalized ratio (INR) OR prothrombin time $\leq 1.5 \times$ ULN unless participant is receiving anticoagulant therapy as long as prothrombin time or aPTT is within therapeutic range of intended use of anticoagulants
- h. Phosphorus < 1.5 ULN

7. Adequate recovery from the side effects of any prior therapy for nonmetastatic disease (generally defined as recovery of all AEs due to \leq Grade 1 or baseline; however, patients with \leq Grade 2 neuropathy, anemia, alopecia, and skin pigmentation may be eligible).
8. Have provided archival tumor tissue sample or newly obtained core or excisional biopsy of a tumor lesion not previously irradiated. Formalin-fixed, paraffin embedded tissue blocks are preferred to slides. Newly obtained biopsies are preferred to archived tissue.
9. Have a measurable disease per RECIST 1.1, as assessed by the local site Investigator/radiology. Lesions situated in a previously irradiated area are considered measurable if progression has been demonstrated in such lesions.
10. A male patient must agree to use contraception during the treatment period and for at least 6 months following the last dose of study treatment.
11. A female patient is eligible to participate if she is not pregnant, not breastfeeding, and at least one of the following conditions applies:
 - a. Not a woman of childbearing potential (WOCBP).
 - b. A WOCBP who agrees to follow contraceptive guidance during the treatment period and for at least 6 months after the last dose of study treatment.
 - c. A WOCBP who has a negative serum pregnancy test within 7 days prior to treatment.
12. Ability to take medications orally (feeding tube is not permitted).
13. Willing and able to comply with scheduled visits and study procedures.

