8.1.3.1. Target and Non-Target Response Assessments

Assessments will be based on the definitions for target and non-target lesions described in [Table 11](#).

Table 11: Target and Non-target Lesions

TARGET LESIONS	
Lesions Response:	Definition:
Complete Response (CR)	Disappearance of all target lesions. Any pathological lymph node must have reduction in short axis to <10 mm
Partial Response (PR)	At least a 30% decrease in the sum of diameters of the target lesions, taking as a reference the baseline sum diameters
Progressive Disease (PD)	At least a 20% increase in the sum of diameters of the target lesions, taking as a reference the smallest sum on study, including the baseline sum. In addition to the relative increase of 20%, the sum must also demonstrate an absolute increase of at least 5 mm. Definitive new lesion presence also indicates progression.
Stable Disease (SD)	Neither sufficient shrinkage to qualify for PR nor sufficient increase to qualify for PD, referencing the smallest sum diameters while on study.
NON-TARGET LESIONS	
Lesions Response:	Definition:
Complete Response (CR)	Disappearance of all non-target lesions and normalization of tumor marker level. All lymph nodes must be non-pathological in size (<10-mm short axis)
Partial Response (PR)	Persistence of one or more non-target lesion(s) and/or maintenance of tumor marker level above the normal limits
Progressive Disease (PD)	Unequivocal progression of existing non-target lesions (see following definition).

Abbreviations: CR=complete response; PD=progressive disease; PR=partial response; SD=stable disease

Progression in Non-target Disease: There must be an overall level of substantial worsening in non-target disease such that, even in the presence of SD or PR in target disease, the overall tumor burden has increased sufficiently to be considered as PD.

Because worsening in non-target disease cannot be easily quantified, a useful test that can be applied when assessing patients for unequivocal progression is to consider if the increase in overall disease burden based on the change in non-measurable disease is comparable in magnitude to the increase that would be required to declare PD for measurable disease (ie, an increase in tumor burden representing an additional 73% increase in “volume” [which is equivalent to a 20% increase in the diameter of a measurable lesion]).

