8.1.4. Objective Response Assessment

Assessments will be based on the definitions provided in [Table 12](#) and [Table 13](#). Since this is a non-randomized study, all responses (CR/PR) must be confirmed.

Table 12: Time Point Response for Patients with Target (\pm Non-target) Disease

Target Lesions	Non-Target Lesions	New Lesions	Objective Response
CR	CR	No	CR
CR	Non-CR/Non-PD or Not all evaluated	No	PR
PR	Non-PD or Not all evaluated	No	PR
SD	Non-PD or Not all evaluated	No	SD
Not all evaluated	Non-PD	No	NE
PD	Any	Yes or No	PD
Any	PD	Yes or No	PD
Any	Any	Yes	PD

Table 13: Time Point Response for Patients with Only Non-target Disease

Non-Target Lesions	New Lesions	Objective Response
CR	No	CR
Non-CR/Non-PD	No	SD
Not all evaluated	No	NE
Unequivocal PD	Yes or No	PD
Any	Yes	PD

Abbreviations: CR=complete response; NE=not evaluable; PD=progressive disease; PR=partial response; SD=stable disease

The efficacy evaluation criteria described above will be used to derive the primary and secondary efficacy endpoints as defined in [Section 2](#).

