2. STUDY OBJECTIVES AND ENDPOINTS

2.1. Study Objectives

2.1.1. Primary Objective

The primary objective of this study is to assess the antitumor activity of the combination of futibatinib and pembrolizumab in patients with unresectable locally advanced or metastatic UC who are not candidate to receive a platinum-based treatment regimen as measured by objective response rate (ORR).

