5.3.2. Demographic and Other Baseline Characteristics

The following baseline characteristics will be summarized by cohort. Listings will also be provided.

- Age
- Age category (< 65, ≥65)
- Sex (Male, Female)
- Ethnicity (Hispanic/Latino, Not Hispanic/Latino, Unknown)
- Race (American Indian/Alaska Native, Asian, Black/African American, Caucasian/White, Native Hawaiian/Other Pacific Islander, Other)
- Region (North America, Europe)
- ECOG PS (0, 1)
- Baseline height
- Baseline weight
- Location of Primary Tumor (Bladder, Upper Tract)
- Sub-type of Location of Primary Tumor (Basal-squamous, Luminal-papillary, Luminal-infiltrated, Luminal, Neuronal, Unknown)
- Any metastases (Yes, No)
- Prior surgery (Yes, No)
- Prior radiotherapy (Yes, No)
- Prior systemic anti-cancer therapy (Yes, No)
- Number of prior lines of systemic therapy
- *FGFR* Status

- *FGFR1* Fusion, Rearrangement, or Translocation (Yes, No)
- *FGFR2* Fusion, Rearrangement, or Translocation (Yes, No)
- *FGFR3* Fusion, Rearrangement, or Translocation (Yes, No)
- *FGFR3* mutation other than Fusion, Rearrangement, or Translocation (Yes, No)
- *FGFR4* Fusion, Rearrangement, or Translocation (Yes, No)

All collected information for cancer diagnosis will be summarized and listed.

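### A patient whose only measurable lesion is the primary tumour can enter the trial but has no target lesion, so cannot score a partial response

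*Protocol*

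**What the plan says.** **Lesion selection.** In Protocol 8.1.2, the target-lesion list tells the reader to take as targets "All measurable lesions up to a maximum of 2 lesions/organ and 5 lesions in total" and makes no exception for the primary. The non-target list in the same section says: "The primary lesion should always be classified as a non-target lesion irrespective of its size and whether or not it can be accurately measured".

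**Entry.** Inclusion criterion 9 (Protocol 4.1) reads: "Have a measurable disease per RECIST 1.1, as assessed by the local site Investigator/radiology". It deals with previously irradiated lesions but does not mention the primary. Criterion 1 begins: "Histologically confirmed advanced or metastatic UC in patients who have not received systemic treatment for advanced metastatic disease". SAP 2.1.1 describes "patients with unresectable locally advanced or metastatic UC", and SAP 5.3.2 tabulates metastases at baseline as present or absent. Metastatic disease is therefore not a condition of entry.

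**Response.** For target lesions, Protocol Table 11 defines PR as "At least a 30% decrease in the sum of diameters of the target lesions" relative to baseline. Protocol Table 12 and SAP Table 4 reach an overall CR or PR only from a target-lesion CR or PR. The protocol adds "Table 13: Time Point Response for Patients with Only Non-target Disease", whose possible results are CR, SD, NE and PD. The SAP has no counterpart to that table.

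**Analysis.** ORR is the proportion with a best overall response of CR or PR in the All Treated Population, by cohort. SAP 5.4.1 rejects the null at 12 or more responders of 20 in Cohort A and 9 or more of 20 in Cohort B.

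**The concern.** The entry criterion and the response criterion use different ideas of measurable disease. A patient with a measurable bladder or upper-tract primary and nothing else measurable meets criterion 9. Under 8.1.2 that patient has no target lesion, so there is no sum of diameters from which a 30% decrease could be calculated. Substantial shrinkage short of complete disappearance cannot be scored as a response, yet the patient stays in the denominator.

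Patients with metastases can be affected too, if their other lesions are all too small or otherwise non-measurable under 8.1.2.

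At stake is the primary endpoint in cohorts of about 20 with a fixed responder count, where one misclassified patient matters. The loss may also be hard to recover afterwards. Section 8.1.2 does not require measurements of other non-target lesions, and nothing asks for a non-target primary to be measured.

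**Working it through.** **Step 1: trace one patient.** Take an unresectable, measurable primary with no measurable metastasis and no node of 15 mm or more in short axis.

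| Stage | Rule | Result |
|---|---|---|
| Entry | Inclusion 9 | Eligible |
| Lesion selection | 8.1.2, non-target list | Primary is non-target; no target lesion |
| Response, protocol | Table 13 | CR, SD, NE or PD; no PR |
| Response, SAP | Table 4 | No row for a patient without target lesions |
| Denominator | All Treated | Counted |

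Table 11 has a non-target row labelled partial response (one or more lesions persist). It gives no overall PR, because Table 13 turns a non-target result that is neither CR nor PD into SD.

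**Step 2: the plan's own figures.** Inputs from Protocol 11.1 and SAP 3.3 and 5.4.1 are n = 20; Cohort A null 35%, target 65%, cut-off r = 12; Cohort B null 25%, target 50%, cut-off r = 9.

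- The exact 90% intervals reproduce: 12/20 gives 39.4% to 78.3%, and 9/20 gives 25.9% to 65.3%.
- Exact power, P(X ≥ r) with X ~ Bin(20, p1), is 76.2% for A and 74.8% for B. The plan says approximately 80%. That gap is a separate matter; the exact values are the baseline here.

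**Step 3: effect of k affected patients.** The documents give neither k nor the share of responses that are CRs, c, so both are assumptions. Affected patients are assumed to share the cohort's true response rate p1 and to count as responders only through CR, with probability c × p1.

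- Expected ORR = [(20 − k) × p1 + k × c × p1] / 20
- Power = Σ over j of P(Bin(k, c × p1) = j) × P(Bin(20 − k, p1) ≥ r − j)

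With c = 0 the power reduces to P(Bin(20 − k, p1) ≥ r). Each affected patient then lowers expected ORR by p1/20: 0.65/20 = 3.25 points in A and 0.50/20 = 2.5 points in B.

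| k of 20 | A: expected ORR, c = 0 | A: power, c = 0 | A: power, c = 0.3 | B: expected ORR, c = 0 | B: power, c = 0 | B: power, c = 0.3 |
|---|---|---|---|---|---|---|
| 0 | 65.0% | 76.2% | 76.2% | 50.0% | 74.8% | 74.8% |
| 1 | 61.75% | 66.6% | 69.5% | 47.5% | 67.6% | 69.8% |
| 2 | 58.5% | 54.9% | 61.7% | 45.0% | 59.3% | 64.2% |
| 3 | 55.25% | 42.0% | about 53% | 42.5% | 50.0% | 58.1% |

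One entry can be checked by hand. For B with k = 3 and c = 0, 17 patients remain at p = 0.5, and 9 or more of 17 has probability exactly one half by symmetry.

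**The case against.** **The number affected may be zero.** This stands. An affected patient needs a measurable primary in place and nothing else measurable. Locally advanced disease is not the same as primary-only disease, because a node of 15 mm or more can still be a target. The present/absent item for metastases shows that the SAP allows for patients without them, not that primary-only patients are expected.

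**The rule looks deliberate.** Its wording shows that measurable primaries were considered, and 8.1.2 prefers targets that can be measured reproducibly. The two lists can be read as a general rule and a specific exception. That is a fair reading of 8.1.2, but it does not repair the mismatch with criterion 9, which still admits the patient.

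**The error is conservative.** This also stands. Blocking PR can only lower the responder count, so the cost is power and an underestimated ORR.

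**Stronger readings.** Three are tempting, and the documents do not support them:

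- *That ORR is biased downward as a matter of fact.* The bias exists only if such patients enrol, and then only by the PR share of their responses, since Table 13 still allows CR.
- *That these patients will definitely be scored SD.* Protocol 8.1.3 defers to the SAP, and the SAP leaves them unclassified. SD is the likelier result, because Table 13 leads there and 8.1.4 ties its criteria to the endpoints.
- *That the 35% and 25% benchmarks were obtained under a different lesion rule.* The documents do not give their source, so nothing can be said either way.

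**Conclusion.** The mismatch is real. An eligible patient whose only measurable lesion is the primary cannot score PR, has no defined response under SAP Table 4, and still counts in the denominator. The defect lies in a stated rule of the primary endpoint.

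Its size is unknown because the documents give no count. The first affected patient in 20 costs at most 9.7 points of power in Cohort A (76.2% to 66.6%, from unrounded values) and 7.2 points in Cohort B (74.8% to 67.6%). With 30% of responses as CRs, the same patient costs about 6.7 points (76.2 − 69.5) and 5.0 points (74.8 − 69.8). All these figures assume 20 patients in the cohort, although each may hold up to 26, and the cohort's response rate in affected patients. The zero-CR figures are a worst case, not a forecast.

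Because the count may be zero and the direction is conservative, this is a point that should be fixed; it does not invalidate the design.

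**What to change.** Make the entry and response criteria agree by one of two routes.

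1. **Change entry.** Amend inclusion criterion 9 to require at least one measurable lesion other than the primary. This keeps 8.1.2 as it is and gives local readers no new choice. Cost: a few patients become ineligible.
2. **Change lesion selection.** Replace the sentence on the primary in 8.1.2 with a rule that leaves no discretion, for example: *the primary is a non-target lesion unless it is the only measurable lesion, in which case it must be the target lesion.* Wording that merely permits the primary as a target should be avoided, because it would let local readers in an open-label trial choose. Cost: primaries may be measured less reproducibly than metastases, and baseline scans of any such patients already enrolled would need re-measuring.

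Under either route, add the matching exception to the target-lesion list so that the two lists in 8.1.2 agree, and state in SAP 5.4.1 how a patient without target lesions is classified, either by adopting Protocol Table 13 or by an explicit rule. The work is one sentence in a protocol amendment, the matching lesion-list wording and a short SAP addition. No extra scans are needed.
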